APPENDIX VII. REFERENCES 36

LIST OF ABBREVIATIONS

AE	adverse event
AK	actinic keratosis
ALA	aminolevulinic acid
BLU-U	blue light phototherapy illuminator
CFR	Code of Federal Regulations
CRF	case report form
DMC	Data Monitoring Committee
DSMB	Data Safety Monitoring Board
FDA	Food and Drug Administration
GCP	Good Clinical Practice
HCl	Hydrochloride
HIPAA	Health Insurance Portability and Accountability Act of 1996
ICF	informed consent form
ICH	International Conference on Harmonisation
IEC	Independent Ethics Committee
IRB	Institutional Review Board
LSR	Local skin reaction
PDT	photodynamic therapy
PpIX	protoporphyrin IX
PI	Principal Investigator
SAE	serious adverse event
SCC	squamous cell carcinoma

PROTOCOL SYNOPSIS

TITLE	Tolerability and efficacy of daylight aminolevulinic-acid-photodynamic therapy (ALA-PDT) compared with conventional ALA-PDT for treatment of actinic keratosis on the face or scalp
SPONSOR	Investigator Initiated Protocol
FUNDING ORGANIZATION	Sun Pharmaceutical Industries Ltd
NUMBER OF SITES	1
RATIONALE	
Actinic keratoses (AK) are common precancerous skin lesions that arise on sun-damaged skin. Treatment is aimed at preventing progression to cutaneous squamous cell carcinoma (SCC). First-line therapy for clinically apparent lesions includes cryotherapy and curettage; and field therapy options are topical 5-fluorouracil, imiquimod, ingenol mebutate, and photodynamic therapy (PDT). PDT involves the topical application of aminolevulinic acid (ALA), or one of its derivatives, as a photosensitizing agent. In response, rapidly proliferating, dysplastic cells preferentially accumulate protoporphyrin IX (PpIX). When PpIX is activated by blue or red light, singlet oxygen species are produced, resulting in cell death. PDT is beneficial due to its brief treatment course and efficacy in clearing AK. However, its main drawbacks are the adverse effects of pain, burning, pruritus, erythema, crusting, and inflammation associated with treatment. While conventional PDT uses red or blue artificial light to activate a high concentration of accumulated protoporphyrins, daylight PDT uses natural daylight to activate lower levels of protoporphyrins in a continuous manner. Daylight PDT, when compared with conventional PDT, has been associated with significantly less pain while achieving comparable efficacy for the treatment of AK. Daylight PDT is also more cost-effective and reduces the amount of time spent in clinic. Previous randomized studies comparing daylight PDT with conventional PDT have largely used methyl-aminolevulinate as the photosensitizer, have been intra-individual comparative studies, and have been performed in Nordic countries. Because the effective light dose from natural daylight depends on geographic location and seasonal and weather changes, randomized trials in different geographic and environmental conditions are of interest. The proposed randomized clinical trial investigates the tolerability and efficacy of daylight ALA-PDT for the treatment of AK in San Francisco for the first time; subjects will be randomized to various treatment arms, as opposed to previous split-face and intra-individual studies.

STUDY DESIGN	Randomized (1:1:1), single-blind controlled trial with parallel group design
PRIMARY OBJECTIVE	To determine whether daylight PDT affords a reduction in treatment symptoms of pain, burning, and pruritus as measured by 1) symptom level during the treatment period and 2) pain at the end of treatment exposure.
SECONDARY OBJECTIVES	
To determine efficacy in clearance of AK at 12 weeks as measured by 1) Reduction in number of AKs and 2) Proportion of patients with partial and complete clearance of AKs.
 
To determine whether daylight PDT affords a reduction in local skin reaction to treatment.
 
To determine whether daylight PDT enables a faster resolution of pain and local skin response during the follow-up period.

NUMBER OF SUBJECTS	30; 10 in each treatment arm
SUBJECT SELECTION CRITERIA	
Inclusion Criteria:
 
 • Adults at least 18 years old. • Subjects must be able to read, sign, and understand the informed consent • Subjects have at least 4 and no more than 20 clinically typical, visible actinic keratoses in the target treatment area on the face or scalp. • Subject must be willing to forego any other treatments for AK in the treatment area on the face or scalp, during the study period, and for 14 days prior to screening; including cryotherapy, topical 5-fluorouracil, imiquimod, and ingenol mebutate. • Subjects who have previously received PDT must undergo at least an 8-week washout period prior to enrollment in study. • Subject must be willing and able to participate in the study and to comply with all study requirements including concomitant medication and other treatment restrictions, and telephone interview. • If subject is a female of childbearing potential she must have a negative urine pregnancy test result prior to study treatment initiation and must agree to use an approved method of birth control while enrolled in the study. Women who are pregnant, lactating, or planning to become pregnant during the study

	
period are excluded from the study.
 
Exclusion Criteria:
 
 • Subjects with any dermatologic disease in the treatment area that may be exacerbated by the treatment proposed or that might impair the evaluation of AKs. • Subjects who are currently participating in another clinical study or have completed another clinical study with an investigational drug or device on the study area within 30 days prior to study treatment initiation. • Subjects with any medical condition that, in the opinion of the investigator, makes the patient unsuitable for the trial.

TEST PRODUCT, DOSE, AND ROUTE OF ADMINISTRATION
	
Study medication—Aminolevulinic acid HCl topical solution 20% (Levulan Kerastick)
 
Study device—BLU-U blue light phototherapy illuminator
 
After preparation of the treatment area with acetone, one stick of Levulan (containing 354 mg ALA HCl) will be topically applied to the treatment area (face or scalp). Subjects will be randomized to one of three treatment arms to receive BLU-U exposure and/or daylight exposure. Treatment arms are as follows:
 
A. Conventional arm: Acetone preparation, ALA topical application, 1hour incubation, 16 minutes 40 seconds (16:40) BLU-U exposure, application of sunscreen.
 
B. Combination arm: Acetone preparation, ALA topical application, 15 minute incubation, 16:40 BLU-U exposure, application of sunscreen, 45 minute daylight exposure.
 
C. Daylight arm: Acetone preparation, ALA topical application, 15 minute incubation, application of sunscreen, 1 hour daylight exposure.

DURATION OF SUBJECT PARTICIPATION AND DURATION OF STUDY
	
Subjects will be on study for up to 115 days.
 
Screening: up to 30 days
 
Treatment: 1 day
 
Follow-up: 84 days
 
The total duration of the study is expected to be 16 months. Approximately 12 months for subject enrollment and 4 months for treatment and final subject follow-up.

CONCOMITANT MEDICATIONS	Allowed: Bland topical emollients such as Eucerin, Cetaphil. Prohibited: Any topical prescription medication on the treatment area during the study.
EVALUATIONS	
PRIMARY ENDPOINT	Primary objective is to determine whether daylight PDT affords a reduction in treatment symptoms of pain, stinging/burning, and itching/pruritus. Primary endpoints will be: 1) peak symptom level and composite score during the treatment period 2) symptom level and composite score at the end of treatment exposure.
SECONDARY ENDPOINTS	1) To determine efficacy in clearance of AK at 12 weeks: A. percent reduction in number of AKs from baseline to 12 weeks B. proportion of subjects with complete and partial clearance of AKs as described above 2) To determine whether daylight PDT affords, at end of treatment, a reduction in composite local skin reaction 3) To determine whether daylight PDT has a faster resolution of composite treatment symptoms and local skin response during days 8, 29, and 84.
STATISTICS Primary Analysis Plan	Symptom level over time during the treatment period will be graphed for visualization along the three axes of pain, stinging/burning, and itching/pruritus as well as a composite symptom score. Peak symptom level during the treatment period and pain at the end of treatment exposure will be compared between the conventional treatment arm (A), the combination treatment arm B), and the daylight treatment arm (C), with unpaired t-tests. Percent reduction in the number of actinic keratoses and proportions of patients with partial and complete clearance of actinic keratoses will be presented descriptively and visualized as histograms. We will compare the percent reduction in the number of AKs and the proportions of patients with clearance between the conventional treatment arm (A) and the combination treatment arm B), and between the conventional treatment arm (A) and the daylight treatment arm (C), using unpaired t-tests.

	
All analyses will be based on the intent-to-treat (ITT) population. In the ITT population, patients will be counted in the treatment group upon randomization, regardless of receiving any dose of study medication. For efficacy analysis, all missing values due to patient early termination from the study will be imputed using last observation carried forward (LOCF) method, as appropriate. For each patient, the Baseline values will be defined as those values recorded at Day 1 prior to dosing. Patients who are lost-to-follow-up after Baseline will be included to the ITT population carrying forward their Baseline values.

Rationale for Number of Subjects
	
This is a small descriptive study. With ten subjects in each group, we will be powered to detect a 1.25-point difference in pain (pain scale 1-10) with a two-sided alpha of 0.05 and a power of 0.8.

1 BACKGROUND

Photodynamic therapy (PDT) is one field therapy option for the treatment of actinic keratosis (AK). PDT involves the topical application of aminolevulinic acid (ALA), or one of its derivatives, as a photosensitizing agent. In response, rapidly proliferating, dysplastic cells preferentially accumulate protoporphyrin IX (PpIX). When PpIX is activated by blue or red light, singlet oxygen species are produced, resulting in cell death. PDT is beneficial due to its brief treatment course, ease of patient compliance, and efficacy in clearing AK. However, its main drawbacks are the adverse effects of pain, burning, pruritus, erythema, crusting, and inflammation associated with treatment. Daylight PDT, when compared with conventional PDT, has been associated with significantly less pain while achieving comparable efficacy for the treatment of AK in randomized trials from Nordic countries and Australia.¹⁻²

1.1 Overview of Clinical and Non-Clinical Studies

Randomized trials, mostly from Nordic countries (Denmark, Norway, Sweden, Finland)^{1, 3-10} and one from Australia,² have supported the use of daylight PDT for the treatment of AK. One case series from the United States documented the Southern California experience with daylight PDT.¹¹ PDT has been associated with significantly less pain compared with conventional PDT, while maintaining efficacy comparable to that of conventional PDT for treatment of AK.^{1,2,11} Post-treatment cosmesis with daylight PDT has been excellent.¹¹ The effective dose of sunlight required for AK clearance by daylight PDT is unclear. Effective light dose from natural sunlight has been shown to be highly variable based on geographic location, weather, and time of year.¹²⁻¹³

2 STUDY RATIONALE

Actinic keratoses (AK) are common precancerous skin lesions that arise on sun-damaged skin. Treatment is aimed at preventing progression to cutaneous squamous cell carcinoma (SCC). First-line therapy for clinically apparent lesions includes cryotherapy and curettage; and field therapy options are topical 5-fluorouracil, imiquimod, ingenol mebutate, and photodynamic therapy (PDT). PDT involves the topical application of aminolevulinic acid (ALA), or one of its derivatives, as a photosensitizing agent. In response, rapidly proliferating, dysplastic cells preferentially accumulate protoporphyrin IX (PpIX). When PpIX is activated by blue or red light, singlet oxygen species are produced, resulting in cell death. PDT is beneficial due to its brief treatment course and efficacy in clearing AK. However, its main drawbacks are the adverse effects of pain, burning, pruritus, erythema, crusting, and inflammation associated with treatment. While conventional PDT uses red or blue artificial light to activate a high concentration of accumulated protoporphyrins, daylight PDT uses natural daylight to activate lower levels of protoporphyrins in a continuous manner. Daylight PDT, when compared with conventional PDT, has been associated with significantly less pain while achieving comparable efficacy for the treatment of AK. Daylight PDT is also more cost-effective and reduces the amount of time spent in clinic. Previous randomized studies comparing daylight PDT with conventional PDT have largely used methyl-aminolevulinate as the photosensitizer, have been intra-individual comparative studies, and have been performed

in Nordic countries. Because the effective light dose from natural daylight depends on geographic location and seasonal and weather changes, randomized trials in different geographic and environmental conditions are of interest. The proposed randomized clinical trial investigates the tolerability and efficacy of daylight ALA-PDT for the treatment of AK in San Francisco for the first time; subjects will be randomized to various treatment arms, as opposed to previous split-face and intra-individual studies.

2.1 Risk / Benefit Assessment

The risks of aminolevulinic acid HCl are primarily local site reactions such as pain, erythema, burning, pruritus, and crusting. These typically begin on day 1 of treatment. Adverse reactions reported in >10% of patients treated with aminolevulinic acid were erythema, crusted skin, desquamation, burning, stinging, hyperpigmentation, hypopigmentation, pruritus, skin erosion. In 1-10% of treated patients, edema, dysesthesia, local flare, urticaria, localized vesiculation, drug eruption, dermal ulcer, scabbing, excoriation, oozing, hemorrhage, localized tenderness, or local pain were reported. As mucous membrane irritation and ocular injury are risks of treatment, the eyes and mucous membranes will be avoided. During artificial light treatment, the subject, health care personnel, and all present will wear appropriate eye protection; all will be counseled to avoid looking directly at the light source. Due to photosensitization associated with treatment, patients will be advised to avoid sunlight and prolonged or intense light that is not part of the treatment regimen for 40 hours.

Photodynamic therapy with ALA has accepted benefits for the treatment of AK which outweigh the risks. Other field treatments require a longer duration of therapy and require patient compliance at home. Participants in this study will benefit from ALA-PDT, either illuminated by daylight or artificial blue light via BLU-U blue light phototherapy illuminator.

3 STUDY OBJECTIVES

3.1 Primary Objective

To determine whether daylight PDT affords a reduction in treatment symptoms of pain, stinging/burning, and itching/pruritus.

3.2 Secondary Objectives

The secondary objects are (1) to determine efficacy in clearance of AK at 12 weeks; (2) to determine whether daylight PDT affords a reduction in local skin reaction to treatment; (3) to determine whether daylight PDT has a faster resolution of treatment symptoms and local skin response during the follow-up period.

4 STUDY DESIGN

4.1 Study Overview

This is a randomized (1:1:1) controlled trial with parallel group design. Thirty adult subjects are planned; with 10 subjects in each of three treatment arms.

Screening data will be reviewed to determine subject eligibility. Subjects who meet all inclusion criteria and none of the exclusion criteria will be entered into the study.

The following medications and devices will be used:

- (1) Aminolevulinic acid HCl topical solution 20% (Levulan Kerastick)
- (2) BLU-U blue light phototherapy illuminator

Three treatment arms to be compared are as follows:

- A. Conventional arm:** Acetone preparation, ALA topical application, 1 hour incubation, 16:40 BLU-U exposure, application of sunscreen.
- B. Combination arm:** Acetone preparation, ALA topical application, 15 minute incubation, 16:40 BLU-U exposure, application of sunscreen, 45 minute daylight exposure.
- C. Daylight arm:** Acetone preparation, ALA topical application, 15 minute incubation, application of sunscreen, 1 hour daylight exposure.

Total duration of subject participation will be up to 115 days. Total duration of the study is expected to be 16 months.

5 CRITERIA FOR EVALUATION

5.1 Primary Efficacy Endpoint

The primary efficacy endpoint will be (1) symptom level during the treatment period and (2) pain at the end of treatment exposure.

With these endpoints, we will be able to determine whether daylight PDT offers a reduction in treatment symptoms of pain, burning, and pruritus.

5.2 Secondary Efficacy Endpoints

The secondary efficacy endpoints are efficacy, local skin reaction to treatment, and symptoms and local skin response during follow-up period.

- 1) Efficacy in clearance of AK at 12 weeks:
 - A. percent reduction in number of AKs from baseline to 12 weeks
 - B. proportion of subjects with complete and partial clearance of AKs as described above.
- 2) To determine whether daylight PDT affords, at end of treatment, a reduction in composite local skin reaction

- 3) To determine whether daylight PDT has a faster resolution of composite treatment symptoms and local skin response during days 8, 29, and 84.

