9.1.7 Local Skin Reaction (LSR)

Local skin reaction based on known response to PDT (Levulan package insert) will be graded by visual assessment on a custom 4 point scale where 0=none, 1=mild, 2=moderate, 3=severe. Each of the following four reactions will be graded: erythema, vesiculation/postulation, crusting/scabbing/erosion, and edema/swelling. A composite

score will be calculated (range 0-16). LSR assessment will be performed at days 1, 8, 29, and 84.

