9.1.8 Symptom assessment

The patient symptom assessment will measure three axes: pain, stinging/burning, and itching/pruritus. Each of these three will be scored by patient report on a numeric scale (0= none, 10= worst possible). Each symptom will be scored and a composite score will be calculated (range 0-30). All subjects will have symptom assessments at 15, 30, 45, 60, and 75 minutes (Table 2). These times allow equivalent assessments relative to medication application regardless of treatment protocol.

A Universal Pain Assessment Tool demonstrating the numeric scale, verbal descriptor scale, and activity tolerance scale will be provided to assist patients in selecting their pain level (Appendix IV).

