10.3 Visit 3 (Day 3, telephone)

1. Record any Adverse Events
2. Symptom assessment
3. Skindex-16

10.4 Visit 4 (Day 8)Unblinded investigator:

1. Record changes to concomitant medications.
2. Record any Adverse Events
3. Symptom assessment
4. Record Skindex-16
5. Photography of treatment area.

Blinded investigator:

6. Perform abbreviated physical examination.
7. Perform AK count
8. Record LSR

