10.5 Visit 5 (Day 15, telephone)

1. Record any Adverse Events
2. Symptom assessment
3. Skindex-16

10.6 Visit 6 (Day 29)Unblinded investigator:

1. Record changes to concomitant medications.
2. Record any Adverse Events.
3. Symptom assessment
4. Skindex-16
5. Photography of treatment area.

Blinded investigator:

6. Perform abbreviated physical examination
7. Perform an AK count (blinded investigator)
8. Perform a local skin response assessment (blinded investigator)

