APPENDIX I. SCHEDULE OF STUDY VISITS

	Screening (Day -29 to Day 1)	Day 1 (may be combined with screening)	Day 3 (telephone)	Day 8	Day 15 (telephone)	Day 29	Day 84
Informed consent	X						
Medical history	X						
Concomitant medications	X	X		X		X	X
Adverse events		X	X	X	X	X	X
Urine Pregnancy test (if applicable)	X						
Randomization		X					
ALA-PDT		X					
AK count	X	X		X		X	X
AE assessment		X	X	X	X	X	X
Local Skin Reaction		X (pre and post)		X		X	X
Symptom Assessment		X	X	X	X	X	X
Skindex-16		X	X	X	X	X	X
Photography		X		X		X	X

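### The symptom-resolution endpoint names only Days 8, 29 and 84, although symptoms are also scored on Days 3 and 15, so it can miss a difference if symptoms fade within days

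*Combined protocol and SAP*

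**What the plan says.** The third secondary objective (section 3.2) is to find out whether daylight treatment gives "faster resolution of treatment symptoms and local skin response during the follow-up period". The matching endpoint, in the synopsis and in section 5.2, narrows this to "faster resolution of composite treatment symptoms and local skin response during days 8, 29, and 84".

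The two components have different schedules:

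- **Local skin response.** Section 9.1.7 describes a visual grading and states "LSR assessment will be performed at days 1, 8, 29, and 84". The three follow-up days are exactly those in the endpoint.
- **Symptoms.** Section 9.1.8 covers pain, stinging/burning and itching, and says "Each of these three will be scored by patient report on a numeric scale"; the composite runs from 0 to 30. Sections 10.3 and 10.5 include this assessment in the Day 3 and Day 15 telephone visits. The "Symptom Assessment" row of Appendix I is marked at Days 1, 3, 8, 15, 29 and 84.

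Section 10 allows 3 days either side of every visit. Section 15.4 promises a summary by secondary endpoint but does not define resolution or list visits for it. Section 15 defers detail to an SAP to be written before the final analysis.

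**The concern.** One list of days has been applied to two measures collected on different schedules. It fits local skin response and is too short for symptoms. No section gives a reason, and none assigns the Day 3 and Day 15 symptom scores to another analysis: the symptom graphs in sections 15.3 and 15.4 cover the treatment period only.

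The question is how fast symptoms go away. On local reactions such as pain, burning and pruritus, section 2.1 says "These typically begin on day 1 of treatment". The first score in the endpoint is nominally seven days after that. If symptoms are mostly gone by then in all arms, a real difference in speed leaves little trace on the named days, while the score that could show it is already in the database.

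**Working it through.** **1. Collection days against endpoint days.**

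| Follow-up day | Days after treatment | Symptoms collected | Skin response collected | In endpoint 3 |
|---|---|---|---|---|
| 3 | 2 | yes (telephone) | no | no |
| 8 | 7 | yes | yes | yes |
| 15 | 14 | yes (telephone) | no | no |
| 29 | 28 | yes | yes | yes |
| 84 | 83 | yes | yes | yes |

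Symptoms lose 2 of 5 scores and skin response loses none. Adding Days 3 and 15 moves the first symptom score from 7 days to 2 days after treatment, and splits the 21-day gap from Day 8 to Day 29 into 7 and 14 days.

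**2. The plan's own figure.** There is none for this endpoint. The 80% power in section 15.6 is for a 1.25-point difference in pain, and no SD is stated, so it cannot be carried over.

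**3. What the omitted days could show.** The documents give onset but no time to resolution, so medians are assumed. With exponential times to resolution, the share unresolved t days after treatment is 0.5^(t/median). For medians of 2 days (conventional) and 1 day (daylight):

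- Day 3: 0.5^(2/2) − 0.5^(2/1) = 0.50 − 0.25 = 0.25
- Day 8: 0.5^(7/2) − 0.5^(7/1) = 0.088 − 0.008 = 0.08

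The same formula gives these gaps in percentage points:

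| Assumed medians, days | Day 3 | Day 8 | Day 15 |
|---|---|---|---|
| 2 v 1 | 25 | 8 | 1 |
| 3 v 1 | 38 | 19 | 4 |
| 4 v 2 | 21 | 21 | 8 |
| 7 v 3 | 19 | 30 | 21 |
| 14 v 7 | 9 | 21 | 25 |

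Day 3 is the most informative day only when resolution is quick. When it is slow, the useful omitted day is Day 15.

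**4. Illustrative power.** Assumptions: 10 per arm; three items averaging 4 of 10 (SD 2) after treatment in both arms; exponential decay with log-normal half-lives (sigma 0.5); daylight halves the half-life; each item rounded; t-test on area under the curve.

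| Half-lives, days | Days 8, 29, 84 | All five days |
|---|---|---|
| 1.5 v 0.75 | 0.16 | 0.62 |
| 2 v 1 | 0.47 | 0.61 |
| 3 v 1.5 | 0.64 | 0.61 |

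The first row is fragile. Rounding only the composite gives 0.38 against 0.55. Letting visits vary within the 3-day window, with each item rounded, gives 0.22 against 0.32.

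**5. Whether area under the curve measures speed.** For exponential decay from score S with half-life h, the area is S × h / ln 2.

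- S = 12, h = 1: 12 × 1 / 0.693 = 17.3
- S = 6, h = 2: 6 × 2 / 0.693 = 17.3

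A milder start and a faster fall give the same area. With identical half-lives and starting scores of 12 and 6, the five-day area test was significant in 33–38% of simulated trials although speed did not differ.

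Time to a composite of 0 is affected less. A score rounds to 0 after h × log2(S/0.5), which is 4.58 half-lives from 12 and 3.58 from 6: 22% shorter, against 50% for the area. A score expressed relative to its end-of-treatment value removes the starting level under this model.

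**The case against.** The best defence is that no test is planned for this endpoint. The study calls itself small and descriptive, section 15.4 promises only a summary, and an SAP is still to come. Nothing forbids showing Days 3 and 15, and the opening of section 5.2 speaks of the follow-up period generally. The larger gap is that resolution is never defined. The visit window also blurs the gain: the Day 3 call may fall as late as Day 6 and the Day 8 visit as early as Day 5.

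Most of this stands, and it limits the weight of the point. It does not remove it: the three days are written into the endpoint in two places, so an SAP that follows the endpoint as written would leave the telephone scores out.

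Two stronger readings are tempting, and neither is supported. A reader might infer that the endpoint cannot show a difference once most subjects score 0 by Day 8. In the simulation with half-lives of 2 and 1 days, 52% and 92% score 0 on Day 8, yet power on the three days is 0.47. A reader might also infer that Day 3 is where the arms differ most. That depends on resolution time, which the documents do not give, and it fails for the slower scenarios above.

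**Conclusion.** The mismatch is a matter of record. Endpoint 3 is narrower than its objective and drops two of five follow-up symptom scores, including the only one in the first week after treatment day, using a day list that fits only the other component.

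The consequence is conditional. The loss can be large if symptoms fade within a few days, is close to nil in the simulation at a conventional-arm half-life of 3 days or longer, and shrinks once visit windows are allowed for. It rests on assumed resolution times, starting scores and spread, none of which the documents supply. The power figures should not be read as an estimate of what this trial loses.

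The point concerns symptoms only. Skin response is not collected on Days 3 and 15, so its days need no change. Because the endpoint is secondary and descriptive, this is a change that should be made, not one on which the trial's main conclusion depends.

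**What to change.** In the synopsis, section 5.2 and the SAP:

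- Assess symptom resolution on Days 3, 8, 15, 29 and 84, and keep Days 8, 29 and 84 for local skin response.
- Use actual assessment dates, because the Day 3 and Day 8 windows overlap.
- Define resolution with a measure of speed, such as time to the first composite score of 0 or change over time relative to the end-of-treatment score. Do not use raw area under the composite, which mixes initial severity with speed. If time to 0 is chosen, show end-of-treatment scores beside it, since it still depends partly on the starting level.
- State how subjects with an end-of-treatment score of 0 are handled, as they have nothing to resolve.
- Report the result descriptively. With 10 per arm, Fisher's exact test at a single visit had at most about 22% power across the resolution scenarios run.

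The cost is a few sentences of text. No visit, question or subject is added. The change should be made before the data are analysed.
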